4.3	Study Enrollment Procedures	20
5	STUDY INTERVENTIONS	21
5.1	Interventions, Administration, Duration	21
5.2	Handling of Study Interventions	22
5.3	Concomitant Interventions	22
6	STUDY PROCEDURES	23
6.1	Schedule of Evaluations	23
6.2	Visit Description	23
6.3	Study Outcomes	25
6.4	Blood Sampling	26
6.5	Special Instructions and Definitions of Evaluations	26
7	MANAGEMENT OF ADVERSE EXPERIENCES	26
8	CRITERIA FOR INTERVENTION DISCONTINUATION	28

A double blinded, phase II, randomized controlled trial to study the effects of simvastatin in patients with uterine leiomyoma.

9	STATISTICAL CONSIDERATONS	28
10	DATA COLLECTION, SITE MONITORING, AND ADVERSE EXPERIENCE REPORTING	30
10.1	Data Collection	31
10.2	Role of Data Management	31
11	HUMAN SUBJECTS	31
11.1	Institutional Review Board/ IEC	31
11.2	Informed Consent	32
11.3	Confidentiality	32
11.4	Study Modification/Discontinuation	32
11.5	Investigator Study File (Regulatory Binder)	32
12	REFERENCES	34
13	INVESTIGATOR STATEMENT	36
	LIST OF TABLES AND FIGURES	
1	Figure 1. Study Design	15
2	Table 1. Detailed Flowchart of Study Assessments	16
	APPENDIX	38
1	Prescribing Information for Simvastatin	
2	HDMA Sheet (Standard Pharmaceutical Product Information)	
3	Safety Data Sheet, SIMVASTATIN TABLETS, USP	

A double blinded, phase II, randomized controlled trial to study the effects of simvastatin in patients with uterine leiomyoma.

SYNOPSIS

Title	A double blinded, phase II, randomized controlled trial to study the effects of simvastatin in subjects with uterine leiomyoma.
Short Title	Treatment of fibroids with simvastatin.
Project Phase	2
Sponsor	None.
Principal Investigator	[name], Department of Gynecology & Obstetrics, Johns Hopkins School of Medicine, Johns Hopkins Bayview Medical Center.
Clinical Site	Johns Hopkins Hospital, Johns Hopkins Bayview Medical Center.
Indication	Uterine leiomyoma/ Fibroids.
Hypothesis	The hypothesis is that treatment of clinically relevant leiomyomas (fibroids) with simvastatin leads to tumor size reduction and symptom improvement through inhibition of cellular proliferation, apoptosis induction and modulation of extracellular matrix and mechanical signaling.
Objectives	
Preliminary Efficacy Objectives:
 
 • Tumor size measured by ultrasound imaging comparing tumor volume pre- and post-study using ultrasound imaging. 
Feasibility Objectives:
 
 • Clinical symptom improvement using validated questionnaires. • Subject retention and satisfaction. • Adherence to the recommended treatment dosing. • Completeness of the outcome measures. 
Safety Objectives:
 
 • Adverse events reporting by organ systems. • Pre and post study blood tests. 
Exploratory Objectives:

A double blinded, phase II, randomized controlled trial to study the effects of simvastatin in patients with uterine leiomyoma.

	
 • Characterize the cellular effects of simvastatin on fibroid cells using TUNEL assay. • Evaluate effects of simvastatin on ECM production and synthesis using immunoblotting techniques.
Sample size	60 females.
Study design	
This is a phase 2 double blinded clinical trial to determine the feasibility, safety, and preliminary efficacy of simvastatin in improving symptoms and reducing size of uterine fibroids.
 
The study will enroll 60 eligible participants; the participants will be randomized into two groups with 30 subjects each. The Study Group receives 40 mg/ day oral simvastatin and the Placebo group receives daily oral placebo for a duration of 12 weeks. The study medication will be dispensed once the participant's eligibility has been established after the screening visit. The participants will have study visits at intervals of 0, 6 and 12 weeks after initiation of the study drug intake.
 
The study nurse will follow up with the subject at regular intervals of 1 week throughout the duration of the study to monitor adverse events and ensure compliance with the study drug.
 
After the 12 week study duration, the subject will undergo hysterectomy or myomectomy and the fibroid sample will be collected for analysis. This will help establish molecular, cellular and histologic effects of the study drug on fibroid tissue.
 
The subject will be followed by the study team at their post operative visits at 2 and 6 weeks during their regular visits with their gynecologist.

Inclusion criteria	
To be eligible, subjects must meet all of these criteria:
 
 • Signed informed written consent. • Gender: female.

A double blinded, phase II, randomized controlled trial to study the effects of simvastatin in patients with uterine leiomyoma.

	
 • Age: 18-55 years at time of signing consent. • BMI of subjects: < 45 kg/m². • Uterine fibroids: 
 • Diagnosed by ultrasound (MRI will be used only if ultrasound is inconclusive). • Number: any number of fibroids. • Location: submucosal or intramural. • At least one fibroid of diameter > 3cm. • Symptoms: one or more of the following symptoms of heavy menstrual bleeding (HMB), defined as: Experienced cyclic (22 to 35 days) abnormal uterine bleeding (heavy or prolonged) in at least 3 of the last 6 menstrual periods, including menstrual bleeding lasting 5 or more days or heavy bleeding per participant recall. Examples of heavy bleeding may include, but are not limited to the following: 
 • Requires the use of double protection to manage menstrual bleeding. • Menstrual bleeding accompanied by the sensation of “gushing” or “flooding”. • Saturates more than 1 tampon or sanitary pad per hour for 3 or more consecutive hours. • Regularly needs to change the tampon or sanitary pad at night or regularly soils bedclothes. • Heavy bleeding that affects work, school, or social activities. • Pelvic pain/ pressure likely caused by fibroids. • Plan for surgery (hysterectomy or myomectomy). • Normal Pap smear within the last year. • Use of contraception during study such as non-hormonal oral contraceptives, intrauterine devices (IUD)/ intrauterine systems (IUS), barrier contraceptives, abstinence or sterilization.
Exclusion criteria	To be eligible, subjects must not meet any of these criteria:

A double blinded, phase II, randomized controlled trial to study the effects of simvastatin in patients with uterine leiomyoma.

	
 • Pregnancy or lactation. • Previous or current uterine, cervical or ovarian cancer. • Current endometrial hyperplasia or history of atypical endometrial hyperplasia. Endometrial biopsy will be done during screening (if not done within last 12 months). • Suspicion of leiomyosarcoma. • Recent rapid growth of fibroids (i.e. doubling in size within 1-6 months period). • Unevaluated gynecologic abnormalities (unexplained vaginal bleeding, cervical dysplasia, or abnormal adnexal/ovarian mass). • Menopausal status. • Surgery is urgently indicated (< 3 months) for medical or social reasons. • Hemoglobin \leq 6 g/dL. • Currently enrolled in another investigational study. • Mental condition or other barrier preventing informed written consent. • Allergy or hypersensitivity to simvastatin. • Current use of simvastatin or other drugs of the same class. • Concomitant administration of strong CYP3A4 inhibitors including itraconazole, ketoconazole, posaconazole, voriconazole, erythromycin, clarithromycin, elithromycin, HIV protease inhibitors, boceprevir, telaprevir, nefazodone, and cobicistat-containing products. • Concomitant administration of gemfibrozil, cyclosporine, or danazol, verapamil, diltiazem, amiodarone, diltiazem, dronedarone, amlodipine, ranozoline, lopitamide, and grapefruit juice. • Active liver disease, which may include unexplained persistent elevations in hepatic transaminase levels.(elevation of AST and/or ALT > 2 s.d. above the normal range at screening visit) • Known increased risk or diagnosis of a myopathy. •
Intervention	Drug: Placebo or Simvastatin 40 mg/day tablets taken orally with water.

A double blinded, phase II, randomized controlled trial to study the effects of simvastatin in patients with uterine leiomyoma.

	Simvastatin Tablets, USP. Both the placebo and the study drug will look similar after being encapsulated by the Investigational Drug Pharmacy at Johns Hopkins.
Dosage	One oral encapsulated tablet daily, 40 mg, Simvastatin Tablets, USP or placebo Starch1500.
Study drug administration	One oral tablet, taken in the evening, at the same time every day with water during the study duration.
Subject follow-up visits	Data will be collected on 0 (initiation), 6 and 12 week follow up visits. Our research coordinator will also call the subjects weekly for compliance (feasibility) and side effects/ adverse events monitoring (safety).
Hysterectomy/ myomectomy	The surgery will be performed as per standard of care. A fibroid sample will be collected after the surgery.
Study duration	12 week treatment period, 18-20 weeks total.
Efficacy parameters	Tumor size: We will compare tumor volume pre and post-study using imaging techniques.
Feasibility parameters	
 • Subject retention: percentage of subjects who complete the study (as opposed to drop-outs). • Completeness of the outcome measures: percentage of subjects for whom treatment efficacy endpoints will be available by the end of the follow-up. • Adherence to the recommended treatment dosing: percentage of subjects who take at least 80% of the doses. • Clinical symptom improvement: We will use the validated uterine fibroid symptom and quality-of-life (UFS—QoL) (2) questionnaires to compare symptoms from pre and post-study assessment.
Safety parameters	
 • Percentage of adverse events (AE) and serious adverse events (SAE) by organ systems, including signs/symptoms, laboratory values, and clinical events. • Lab: We will compare hemoglobin, hematocrit, ferritin, liver enzymes and lipid panel pre and post-study.

A double blinded, phase II, randomized controlled trial to study the effects of simvastatin in patients with uterine leiomyoma.

1. INTRODUCTION

1.1 Background on Condition

Uterine leiomyomas (fibroids) represent a formidable clinical problem. With an incidence of 50-80% of women by age 50 (3), they are the most common tumors of the female reproductive tract (4). They are characterized by smooth muscle cellular proliferation and excessive disordered extracellular matrix. The medical and economic burden of fibroids is significant with estimated annual fibroid-related costs in the US of \$5.9-34.4 billion (5). Although hormonal treatments including oral contraceptives are used, efficacy remains limited. Treatment with Gonadotropin-releasing hormone (GnRH) agonists results in tumor shrinkage (6). However, the effect is usually transient and has significant side effects which prohibits long term use (7). Thus, uterine artery embolization and surgery are required in many cases. In fact, symptomatic fibroids are the most common indication for hysterectomy in the US (8). Myomectomy is a fertility-preserving alternative to hysterectomy but it is an invasive procedure including complications in subsequent pregnancies. Thus, there is an urgent need for a novel long term non-hormonal treatment for uterine leiomyomas.

1.2 Study Hypothesis

We hypothesize that simvastatin has therapeutic effects on leiomyoma through modulating cellular proliferation and extracellular matrix deposition and structure. Clinically, this will be associated with shrinkage of the size of leiomyoma tumors, and possibly with improvement of symptoms.

1.3 Supporting Studies

The compelling data from administrative database (9), animal (10) and in vitro (10) studies strongly suggests a therapeutic role for simvastatin in uterine leiomyomas. Simvastatin has been FDA-approved since 1991, and so, its long term safety profile is well known. (See Appendix 1)

Statin use is associated with a lower risk of uterine fibroids and fibroid-related symptoms

In a nested case-control study using one of the nation's largest administrative insurance databases including a cohort of >190,000 women aged 18-65 years with a diagnosis of hyperlipidemia, we found that statin use is associated with decreased odds of uterine fibroids (adjusted odds ratio: 0.87, 95% confidence interval: 0.85-0.89). Furthermore, in a subanalysis restricted to fibroid cases, statin users were

less likely to have menorrhagia, anemia, pelvic pain, or undergoing myomectomy, compared to nonusers (9).

Simvastatin inhibits tumor growth in a subject-derived xenograft animal model

To examine the effect of simvastatin treatment on uterine leiomyoma in animal model, we used a subject-derived xenograft mouse model. After subcutaneous implantation of estrogen/progesterone pellets, leiomyoma tissues were implanted subcutaneously. Animals were treated for 28 days with simvastatin (20 µg/gm body weight/day) vs vehicle control. Treatment was associated with >40% tumor size reduction compared to controls. Furthermore, simvastatin was associated with lower (>50% reduction) expression of the proliferation marker Ki67 (10).

1.4 Relevance and Priority

The completion of this project will be significant as a successful non-hormonal treatment of uterine leiomyomas which will have an enormous impact on women's health through:

- 1) better quality of life through symptom improvement;
- 2) avoiding hysterectomy or myomectomy in women interested in fertility preservation;
- 3) reduction of surgery-related morbidity and mortality; and
- 4) significant savings of healthcare cost through reduced operative procedures and hospital admissions.

2. STUDY OBJECTIVES

We will compare the two arms for:

2.1 Preliminary Efficacy Objectives

- 2.1.1 Tumor size: We will compare tumor volume pre- and post-study using ultrasound imaging.

2.2 Feasibility Objectives

- 2.2.1 Clinical symptom improvement: We will use the validated uterine fibroid symptom and quality-of-life (UFS—QoL) (2) questionnaires to compare symptoms from pre and post-study assessment.
- 2.2.2 Subject retention: percentage of subjects who complete the study (as opposed to drop-outs).

- 2.2.3 Adherence to the recommended treatment dosing: percentage of subjects who take at least 80% of the doses.
- 2.2.4 Completeness of the outcome measures: percentage of subjects for whom treatment efficacy endpoints will be available by the end of the follow-up.

2.3 Safety Objectives

- 2.3.1 Percentage of adverse events (AE) and serious adverse events (SAE) by organ systems, including signs/symptoms, laboratory values, and clinical events.
- 2.3.2 Lab: We will compare hemoglobin, hematocrit, ferritin, liver enzymes and lipid panel pre and post study.

2.4 Exploratory Objectives

- 2.4.1 Characterize the cellular effects of simvastatin on fibroid cells using TUNEL assay.
- 2.4.2 Evaluate effects of simvastatin on ECM production and synthesis using immunoblots.

3. STUDY DESIGN

3.1 Study Structure

This is a double blinded, phase 2 clinical study to determine the feasibility, safety and preliminary clinical efficacy of simvastatin in women with symptomatic fibroids that are candidates for, and are seeking surgical management (hysterectomy/ myomectomy) for the treatment of fibroid related symptoms.

3.2 Sample Size Determination

We plan to enroll 60 study participants (30 in each arm). With a 20% anticipated withdrawal rate (from prior experience in similar studies), we plan to recruit 72 subjects. Sample size was estimated based on pre-clinical results of tissue effect where we expect a difference of 0.2 (20% effect size). This is a pilot study, and based on a 20% effect size and ability to measure within 0.5 centimeter (sigma) with an alpha of 0.5 and power of 0.8, the sample size is 50 subjects using a two sided t-test. We will enroll 60 subjects, to be conservative, which provides confidence that we will observe a difference, if one exists.

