10.2 Role of Data Management

Interval analysis may be conducted by a statistician. We expect that it may take 5 years to accrue 60 evaluable subjects for analysis and to complete the study procedures. The following types of data and processes will be the main focus for each subject:

- 10.2.1 Verification that informed consent was obtained appropriately prior to any study specific procedures and documented properly.
- 10.2.2 Adherence to protocol eligibility criteria.
- 10.2.3 Compliance with protocol procedures.
- 10.2.4 Documentation of procedures and assessments related to protocol-required safety assessments, evaluation and documentation of adverse events, especially any serious adverse events or withdrawals related to adverse events.
- 10.2.5 Conduct and documentation of study endpoints.
- 10.2.6 Procedures for documenting accountability and appropriate administration of the investigational product.

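### At the stated 20% withdrawal, recruiting 72 leaves about 58 evaluable subjects, not 60, and the protocol uses 60 both as the number randomised and as the number evaluable

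*Protocol*

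**What the plan says.** Section 3.2 (Sample Size Determination) sets a target of 60 participants, 30 in each arm, and continues: "With a 20% anticipated withdrawal rate (from prior experience in similar studies), we plan to recruit 72 subjects". It then reports a calculation after which "the sample size is 50 subjects using a two sided t-test", and presents 60 as a cautious choice relative to that 50.

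Elsewhere 60 appears with two meanings:

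- **Number randomised.** The synopsis (Study design) says "The study will enroll 60 eligible participants; the participants will be randomized into two groups with 30 subjects each". Sections 3.3.1 and 3.3.2 each describe 30 participants randomised to the arm. None of these places mentions 72.
- **Number left for analysis.** Section 10.2 (Role of Data Management) expects that "it may take 5 years to accrue 60 evaluable subjects for analysis". This is also the meaning implied by section 3.2 when it inflates 60 to 72.

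**The concern.** There are two linked problems. First, 72 looks like 60 with 20% added, which is not the number that leaves 60 when 20% of those recruited withdraw. Second, 60 cannot be both the number randomised and the number evaluable unless nobody withdraws, and the protocol expects one in five to do so.

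Withdrawals come directly off the primary analysis. Table 1 schedules ultrasound only at screening and at Visit 4, so a subject who leaves before week 12 has no scheduled post-baseline tumour volume. Section 9 makes the 12-week outcome the primary analysis and rules out imputing primary outcome measures. Retention, adherence and completeness of outcomes are themselves feasibility objectives (section 2.2), so their percentages need a defined starting number. The figure also decides when enrolment stops: at 60 or at 72.

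**Working it through.** **Inputs.** Target 60 (30 per arm), withdrawal 0.20, recruitment 72 and calculated sample size 50, all from section 3.2; 60 randomised from the synopsis and sections 3.3.1 and 3.3.2; 60 evaluable from section 10.2.

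**1. Reproduce the plan's figure.** n × (1 + w) = 60 × 1.20 = 72. This matches exactly, so 72 was obtained by multiplying.

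**2. What 72 leaves.** 72 × (1 − 0.20) = 57.6, or 28.8 per arm. The shortfall against 60 is 2.4.

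**3. What 60 evaluable needs.** n / (1 − w) = 60 / 0.80 = 75. With equal arms, 30 / 0.80 = 37.5, so 38 per arm and 76 in total.

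**4. Withdrawal rate at which 72 would be right.** 1 − 60/72 = 16.7%.

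**5. If 60 is the number randomised.** 60 × 0.80 = 48, or 24 per arm, which is 2 below the stated 50. Sixty leaves 50 only if withdrawal is at most 1 − 50/60 = 16.7%.

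**6. The readings side by side, at 20% withdrawal:**

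| Reading | Randomised | Evaluable | Against 60 | Against 50 |
|---|---|---|---|---|
| 72 randomised | 72 | 57.6 | −2.4 | +7.6 |
| 60 randomised | 60 | 48 | −12 | −2 |
| 72 consented, all losses before randomisation | 57.6 | 57.6 | −2.4 | +7.6 |

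The third reading leaves no allowance for withdrawal after randomisation, which section 8 permits at any time.

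**7. Allowing for chance.** Assume that subjects withdraw independently with probability 0.20. The probability of at least 60 completers from 72 is then about 0.30. For at least 50 from 72 it is about 0.99, and for at least 50 from 60 about 0.32.

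**8. Status of the 50.** The printed inputs are a difference of 0.2, a sigma of 0.5 (standardised difference 0.2 / 0.5 = 0.4) and "with an alpha of 0.5 and power of 0.8". By the normal approximation, the number per arm is 2(z₁₋α/₂ + z₀.₈₀)² / 0.4².

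- With alpha 0.5 as printed: 2(0.674 + 0.842)² / 0.16 = 28.7, so 29 per arm and 58 in total. A t-test calculation that counts both tails gives 26.7, so 27 per arm and 54 in total.
- If alpha 0.05 was meant: 2(1.960 + 0.842)² / 0.16 = 98.1, so 99 per arm and 198 in total (200 by the t-test).

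None of these is 50. That is a separate and larger matter. Here 50 serves only as the protocol's own stated benchmark.

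**The case against.** The strongest reply is that section 3.2 is the governing sample-size text and does add recruits for withdrawal. On that plan about 58 remain, which is 15% above the stated 50 (57.6 / 50 = 1.152). The shortfall of 2.4 against 60 widens a standard error by about 2% (√(60/57.6) = 1.021). It is also smaller than the chance variation in withdrawals, whose standard deviation among 72 is √(72 × 0.2 × 0.8) = 3.4. The 20% is itself only an anticipated rate in a pilot study. All of this stands, and it limits the weight of the point.

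It does not remove the error. The recruitment figure does not deliver the evaluable number at the protocol's own rate. The 30-per-arm randomisation wording is repeated in three places and conflicts with sections 3.2 and 10.2.

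A reader might go further and infer that the trial will finish with 48 subjects, below its requirement, and that describing 60 as cautious is therefore false. The documents do not support that as an unconditional statement. The 48 arises only if enrolment stops at 60 randomised, which means setting aside the 72 in section 3.2. Under the plan to recruit 72, the expected number stays above 50 and the cautious margin over 50 survives. The 58 and the 48 belong to alternative readings and cannot both describe the trial. Being 2 below 50 also says little while the printed inputs do not give 50.

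**Conclusion.** The point holds in limited form. The 72 in section 3.2 is wrong as an allowance for 20% withdrawal: it leaves about 58 evaluable subjects, 2.4 short of the 60 in section 10.2, and would be right only at 16.7% withdrawal or less. Separately, 60 is used for two different quantities, and the protocol must say which it is. The consequence for the stated 50 is conditional: about 58 (above it) if 72 are randomised, about 48 (slightly below it) if only 60 are.

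This rests on the stated 20% applying to the number counted, on withdrawn subjects having no 12-week ultrasound, and on taking 50 at face value. The arithmetic is certain and the effect on precision is small. The ambiguity over when enrolment stops, a difference of 12 subjects, matters more than the 2.4.

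**What to change.** - **Preferred.** Keep 72 and define it as the number randomised (nominally 36 per arm). Restate the expected evaluable number as about 58 (29 per arm).
- **Labels.** Mark each figure as recruited, randomised or evaluable, and use the same set in the synopsis and in sections 3.2, 3.3.1, 3.3.2 and 10.2. The 30-per-arm randomisation wording in the synopsis, 3.3.1 and 3.3.2 has to change.
- **Power.** Restate it at about 58 evaluable, but only after the difference, sigma and alpha in section 3.2 have been corrected, since as printed they do not give 50.
- **Alternative.** If 60 evaluable is to be kept, correct the recruitment figure to 75, or 76 for equal arms.

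The preferred route costs protocol wording and no recruits beyond the 72 already in section 3.2, though that is 12 more than the randomisation wording elsewhere provides for. The alternative adds three recruits to the 72, or four for equal arms.

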3.3.1 Study Group

The 30 participants randomized in this group will intake 40mg / day of simvastatin orally at the same time in the evening, every day for the study duration of 12 weeks prior to undergoing hysterectomy/ myomectomy. The fibroid sample will be collected after the surgery to evaluate the effects of the study medication on the fibroid tissue.

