6. Evaluation of fibroid size (volume) and location by ultrasound and/or MRI (only if ultrasound is inconclusive) by study physicians.

After enrollment the following procedures will be performed:

1. Standardized questionnaires (all attached in the appendix) will be administered to assess:
 - Quality of life and sexual activity questionnaires. These instruments have been used to assess subject's response in treatment of fibroids and are accepted surveys. (Uterine Fibroid Symptom and Health-related Quality of Life Questionnaire (UFS-QOL) and Female Sexual Function Index (FSFI)).
 - Pain (McGill Pain Questionnaire (MPQ) and Visual Analog Scale (VAS)).
2. A baseline ultrasound scan of the uterus with careful measurement of fibroid size in three dimensions (width, height and depth, example 4 cm x 4 cm by 5 cm).

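### Section 3.2 does not support its 80% power claim: alpha is printed as 0.5, and neither the effect nor sigma is on the scale of the volume outcome

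*Protocol*

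**What the plan says.** Section 3.2 takes an expected difference of 0.2 from pre-clinical tissue results. The calculation is "based on a 20% effect size and ability to measure within 0.5 centimeter (sigma"), and it concludes that "with an alpha of 0.5 and power of 0.8, the sample size is 50 subjects using a two sided t-test". It then raises 50 to 60, 30 per arm, and says that this "provides confidence that we will observe a difference, if one exists". For losses it says: "With a 20% anticipated withdrawal rate (from prior experience in similar studies), we plan to recruit 72 subjects".

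The efficacy objective (Section 2.1) is on another scale: "We will compare tumor volume pre- and post-study using ultrasound imaging". Section 4.3 asks for "careful measurement of fibroid size in three dimensions (width, height and depth, example 4 cm x 4 cm by 5 cm"), so a volume can be derived from each scan. Section 9 compares the 12-week outcomes between arms with a Gaussian model and a Wald test.

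On numbers, the Synopsis says "The study will enroll 60 eligible participants; the participants will be randomized into two groups with 30 subjects each", and Section 3.3.1 refers to "The 30 participants randomized in this group" (3.3.2 likewise for placebo). Section 10.2, however, treats 60 as the number of evaluable subjects to be accrued.

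**The concern.** Four things do not fit together.

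- **Alpha.** No usable test has a 50% type I error, and the protocol gives no other alpha for this test.
- **Scale.** The 0.2 has no unit. The 0.5 cm is a linear measurement precision, not a between-subject SD of volume or of volume change. The text does not say whether 20% refers to volume or to diameter.
- **Sample size.** With the ratio 0.2/0.5 and a conventional alpha, 50 subjects is far from what a two-arm t-test needs.
- **Withdrawals.** The allowance multiplies by 1.2 where it should divide by 0.8, and 60 is used both for those randomised and for those evaluable.

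Fibroid size is the primary outcome (Section 6.3), and Section 7 allows the trial to stop after 30 completers if the results establish the primary hypothesis. A reader will therefore rely on the stated power when interpreting a positive or a null result. If the power was never established, a non-significant test cannot be held against the planned 20% effect.

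**Working it through.** **Inputs.** From Section 3.2: difference 0.2, sigma 0.5, alpha 0.5 as printed, power 0.8, two-sided t-test, 30 per arm, 20% withdrawal, 72 recruited. From Section 4.1: at least one fibroid over 3 cm. From Section 4.3: the 4 x 4 x 5 cm example. The alpha of 0.05 is an assumption about what was intended.

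**Formula.** n per arm = 2(z_alpha/2 + z_beta)^2 / d^2 with d = difference/SD. Results below use the exact non-central t unless marked normal.

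**1. The plan's own figure.** d = 0.2/0.5 = 0.4.

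- Alpha 0.5 as printed: 2(0.674 + 0.842)^2 / 0.16 = 28.7 per arm (normal) or 26.7 (t), so 58 or 54 in total, not 50. Power is 79% with 25 per arm and 82% with 30 per arm.
- Alpha 0.05: 2(1.960 + 0.842)^2 / 0.16 = 98.1 per arm (normal) or 99.1 (t), so 100 per arm and 200 in total. Power is 28% with 25 per arm and 33% with 30 per arm.

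Two calculations do land near 50. A one-sample test at d = 0.4 and alpha 0.05 gives (1.960 + 0.842)^2 / 0.16 = 49.1 (normal) or 51.0 (t), but that is not the planned comparison. A two-arm test at d = 0.8 gives 24.5 (normal) or 25.5 (t) per arm, about 50 to 52 in total, but 0.8 is not the stated input. Which was used, if either, is conjecture.

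**2. How much the undefined scale matters.** A 20% volume reduction is a diameter reduction of 1 - 0.8^(1/3) = 7.2%. A 20% diameter reduction is a volume reduction of 1 - 0.8^3 = 48.8%. The centimetre rows below use 0.5 cm as the SD only because the protocol labels it sigma. The geometric mean diameter of 4 x 4 x 5 cm is 80^(1/3) = 4.31 cm.

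| Reading (two-sided 0.05) | d | Per arm for 80% power | Power at 30 per arm |
|---|---|---|---|
| 0.2 is already standardised | 0.2 | 394 | 12% |
| 0.2/0.5 | 0.4 | 100 | 33% |
| d that would give about 50 in total | 0.8 | 26 | 86% |
| 3 cm, 20% of volume: 0.215/0.5 | 0.43 | 86 | 37% |
| 3 cm, 20% of diameter: 0.6/0.5 | 1.2 | 12 | over 99% |
| 4.31 cm, 20% of volume: 0.309/0.5 | 0.62 | 43 | 65% |
| 4.31 cm, 20% of diameter: 0.862/0.5 | 1.72 | 7 | over 99% |

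**3. What 30 per arm supports without any unit.** The effect detectable with 80% power is d = 0.736. The 95% confidence interval half-width is t(0.975, 58) x sqrt(2/30) = 2.002 x 0.258 = 0.517 SD.

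**4. On a log-volume scale.** The protocol gives no SD, so these SDs of log-volume change are assumptions. Detectable reduction = 1 - exp(-0.736 x SD).

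| Assumed SD | Detectable reduction (80% power) | Power for a 20% reduction |
|---|---|---|
| 0.3 | 19.8% | 81% |
| 0.4 | 25.5% | 57% |
| 0.5 | 30.8% | 40% |
| 0.6 | 35.7% | 29% |

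**5. Withdrawals.** 60 x 1.2 = 72, but 72 x 0.8 = 57.6. Keeping 60 needs 60/0.8 = 75. With 28.8 per arm the detectable d is 0.751.

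**The case against.** The strongest reply is that 33% is not the trial's power. It combines a corrected alpha with an uncorrected ratio of a unitless 20% to a length, and at the values actually printed 30 per arm gives 82%. Nor is it shown that 50 is too few: at d = 0.8 a two-arm test needs about that many. The centimetre rows also use as an SD the very figure criticised as measurement precision. If 0.5 cm were the error of each scan, a change would have an SD of at least 0.5 x sqrt(2) = 0.71 cm, and the 3 cm volume reading would fall from 37% to 21%. Finally, this is a pilot, the alpha is probably a misprint, and the withdrawal slip is small.

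Much of this stands. The 33% is illustrative, the centimetre rows show spread rather than estimates, and the origin of 50 is unknown. The withdrawal error moves the detectable d only from 0.74 to 0.75, and 57.6 is still above the stated requirement of 50. A null result could also be read through its estimate and confidence interval.

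None of it rescues the claim. The 82% exists only at an alpha nobody would accept, and correcting the alpha alone leaves d = 0.4 at 33%. That the readings run from 12% to over 99% is itself the defect. Pilot status would excuse giving no power statement; it does not excuse an unsupported one that also promises confidence of seeing a difference.

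**Conclusion.** The concern holds. The stated power of 0.8 does not follow from the stated inputs at any acceptable alpha, and those inputs do not fix the power of a between-arm comparison of volume. With the printed difference and sigma used as d = 0.4 at a two-sided 0.05, power is 33% with 30 per arm, less than half of what is claimed, and 80% would need 200 subjects in total. That figure depends on the reading of d and on 0.05 being the intended alpha. What does not depend on the reading is that 30 evaluable subjects per arm have 80% power for a standardised difference of about 0.74 and estimate the difference to within about 0.52 SD.

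The withdrawal arithmetic is wrong by 3 recruits (72 instead of 75). The dual use of 60 is a real but minor inconsistency.

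**What to change.** Keep the sample size and rewrite Section 3.2:

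1. Correct alpha to 0.05, two-sided.
2. Name the scale of the primary analysis, for example change in log volume, say whether 20% refers to volume or diameter, and give a between-subject SD on that scale with its source.
3. From those inputs, state the power or the detectable difference for 30 per arm. Give d of about 0.74 as the unit-free detectable effect, with 33% at d = 0.4 as an illustration only. Alternatively, justify the size by precision (half-width 0.52 SD). If no SD can be sourced, show a range such as the log-volume table above and label the SDs as assumed.
4. Delete the assurance about observing a difference.
5. Either recruit 75 to keep 60 evaluable, or keep 72 and state about 57 evaluable. Use one number randomised and one number evaluable in the Synopsis and in Sections 3.2, 3.3.1, 3.3.2 and 10.2.

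The cost is protocol wording and possibly a less favourable power statement. Only if 60 evaluable remains the target are 3 more recruits needed.
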